7.1.2.8 Assessment of Disease and Tumor Response

7.1.2.8.1 CLL Response Assessments

Disease assessments or scans performed as part of routine clinical management are acceptable for use as the screening scan if they are of diagnostic quality and performed within 28 days prior to Cycle 1 Day 1.

CT scans of the neck, chest, abdomen, and pelvis will be obtained at screening within 28 days of Cycle 1 Day 1. Follow-up CT scans of the neck should be performed if enlarged lymph nodes (defined as ≥ 1.5 cm) are detected on the screening CT neck scan or if medically indicated by the discretion of the treating physician.

CT scans will be repeated every 3 cycles (approximately 9 weeks) despite any delays in treatment. CT scans will be read locally.

Response will be determined locally according to the iwCLL criteria, using results of the subject's CT scan, hematology laboratory results (complete blood counts), and presence of CLL symptoms as described in Section 12.7. Response assessments should be completed in conjunction with the subject's CT scan schedule.

If medically appropriate, a confirmatory assessment of the initial progression event should be performed within 9 weeks. A CT scan of the neck (if indicated), chest, abdomen and pelvis and hematology laboratory (complete blood counts) will be obtained, and the presence of CLL symptoms will be determined at each response assessment time point.

7.1.2.8.2 Multiple Myeloma Response Assessments:

7.1.2.8.2.1 Myeloma Laboratory Testing Disease Measurements

Baseline

For subjects with MM, collect serum and urine samples within 28 days of Cycle 1 Day 1 for baseline disease assessment. Baseline serum and urine (24 hr) M protein levels will be assessed by electrophoresis and immunofixation. Free light chain (FLC) levels and ratio will also be assessed.

Serum electrophoresis (SPEP)

If serum M protein by electrophoresis (SPEP) ≥ 1 g/dL at baseline, SPEP will be assessed after each cycle.

Urine electrophoresis (UPEP)

If urine M protein (24 hr) by electrophoresis (UPEP) ≥ 200 mg, UPEP (24 hr) will be assessed after each cycle.

FLC

For subjects with non-secretory myeloma (SPEP < 1 g/dL and UPEP < 200 mg/24 hr) at baseline, but serum light chain ≥ 10 mg/dl, serum FLC will be assessed after each cycle.

Best Response

Laboratory assessments should be repeated to confirm best response, including SPEP and UPEP, serum and urine immunofixation, and FLC. Bone marrow biopsy is recommended to confirm CR.

Response will be determined locally according to IMWG criteria [2] described in Section 12.8.

7.1.2.8.2.2 Imaging for Subjects with Myeloma Bone Disease

Skeletal survey by conventional radiography must be performed at screening within 28 days of Cycle 1 Day 1 to determine the extent of the subject's myeloma bone disease. The use of conventional or low dose CT scan or magnetic resonance imaging (MRI) bone survey is acceptable. A skeletal survey performed as standard of care prior to signing consent can be used for screening if performed within 28 days of Cycle 1 Day 1.

During the course of the trial, skeletal surveys should be performed as clinically indicated. If suspected disease progression, the same modality of imaging used at screening should be performed for assessment of progression. The development of a compression fracture does not necessarily exclude antitumor response if not related to disease progression. Bone lesions should be considered as non-measurable disease and recorded as such.

For subjects with extramedullary soft tissue plasmacytomas, an MRI, CT, or positron emissions tomography (PET)/CT should be performed at baseline within 28 days of Cycle 1 Day 1. An MRI, CT, or PET/CT performed as standard of care prior to signing consent can be used for screening if performed within 28 days of Cycle 1 Day 1. During the course of the trial, subsequent imaging should be performed as clinically indicated (whether or not an

extramedullary soft tissue plasmacytoma was present at baseline) and at the time of a CR or stringent CR (sCR) assessment. The same modality of imaging used at screening should be performed for subsequent assessments.

At any time a subject develops bone pain or there is a suspicion of new bone disease or extramedullary soft tissue plasmacytoma indicative of disease progression, appropriate imaging according to clinical practice should be performed to confirm disease progression.

7.1.2.8.3 DLBCL Disease Response Assessment

Disease assessments or scans performed as part of routine clinical management are acceptable for use as the screening scan if they are of diagnostic quality and performed within 28 days prior to Cycle 1 Day 1. CT and PET should be used throughout the trial. For lymphomas that are not PET-avid at screening, PET does not need to be repeated in follow-up assessments.

The site trial team must review pre-trial images to confirm the subject has measurable disease as defined in the inclusion criteria.

PET/CT scans of the chest, abdomen, and pelvis will be repeated every 3 cycles (9 weeks) or when medically indicated despite any delays in treatment.

PET/CT scans of the neck should be performed if enlarged lymph nodes are detected during the PE exam or if otherwise medically indicated by the discretion of the treating physician.

PET/CT scans will be read locally.

Response assessment by CT or PET/CT is based on the Revised Response Criteria for Malignant Lymphoma [3] described in Section 12.9. If complete remission is documented by both CT and FDG-PET, subsequent assessments may be by CT only, with PET used only if relapse or recurrence is suspected. Local reading (investigator assessment with site radiology reading) will be used to determine subject eligibility and for subject management.

Assessment of lymphoma B symptoms should occur with each lymphoma disease response assessment (Section 12.10). If a subject has radiographically progressive disease but is clinically stable and suspicious for pseudo-progression, the subject can continue trial treatment after consultation with the Sponsor. Additionally, the subject should be rescanned within 4 to 6 weeks for confirmation. The subject should discontinue trial treatment if they meet discontinuation criteria described in Sections 5.8.1, 7.1.2.7.2, and 7.1.2.7.3.

7.1.2.9 Biopsy Collection and Correlative Studies Blood Collection

All subjects enrolled into this trial must be able to provide a bone marrow biopsy sample or newly obtained core or excisional biopsy (fine needle aspirate not adequate) to be submitted for characterization. Subjects with rDLBCL must also provide a core or excisional biopsy add of lymph node or extranodal lesion at Screening. If the investigator deems that a biopsy is unsafe or not indicated for other reasons, a Sponsor consultation is required.

Biopsies done previously within 3 months before screening are permitted to be used for this trial. If bone marrow biopsy was performed within 3 months before screening but the subject had anticancer treatment after biopsy, the bone marrow biopsy and aspirate should be repeated.

Biopsy sites should be selected so that subsequent biopsies can be performed at the same location. Tumors that are inaccessible or contraindicated due to subject safety concerns are exempt from this requirement. DLBCL subtypes, GCB, ABC, and unclassified (not fitting the criteria for either ABC or GCB DLBCL subtypes), need to be classified and recorded. Other known pathology and biology parameters, such as T-cell/histiocyte-rich B-cell lymphoma, Epstein-Barr virus positive lymphoma, MYC, BCL2 gene rearrangement, expression and MYC gene alterations, should be recorded if data is available.

Bone marrow and lymph node biopsies will be collected as per [Table 14](#).

Table 14 Bone Marrow or Lymph Node Biopsy Assessments

Tumor type	Timing of Biopsy
CLL: Bone marrow biopsy and aspiration	Screening; to confirm CR, or as clinically indicated
MM: Bone marrow biopsy and aspiration	Screening; to confirm CR, sCR, or as clinically indicated
DLBCL: Lymph node or extranodal lesion biopsy, bone marrow biopsy (aspiration only at screening if bone marrow biopsy was performed >3 months before screening and the subject had a subsequent anticancer treatment).	Screening; to confirm CR (if subject had bone marrow involvement at screening), or as clinically indicated All subjects will have lymph node or extranodal lesion biopsy performed during screening. Bone marrow biopsy/aspirate may be performed during screening or an archived bone marrow will be collected at Screening. Subsequent bone marrow assessments will only be performed in subjects who have bone marrow involvement at screening.

Abbreviations: CLL = chronic lymphocytic leukemia; CR = complete response; DLBCL = diffuse large B-cell lymphoma; MM = multiple myeloma; sCR = stringent complete response.

Tissue for correlative biomarker studies should be collected as per [Table 15](#).

Table 15 Tissue Collection for Correlative Biomarkers Studies

Indication	Timing of Correlative Blood Collection
Whole Blood for RNA/DNA:	Pre-dose on C1D1, pre-dose on C2D1, Discontinuation
Blood for biomarker studies (plasma and serum)	Pre-dose on C1D1, pre-dose on C2D1, Discontinuation
Blood for genetic analysis	Pre-dose on C1D1
CLL: Saliva for genetic analysis	Pre-dose on C1D1

Abbreviations: C1D1 = Cycle 1 Day 1; C2D1 = Cycle 2 Day 1; CLL = chronic lymphocytic leukemia.

7.1.3 Laboratory Procedures/Assessments

Details regarding specific laboratory procedures/assessments to be performed in this trial are provided below. The total amount of blood/tissue to be drawn/collected over the course of the trial (from pre-trial to post-trial visits), including approximate blood/tissue volumes drawn/collected by visit and by sample type per subject can be found in the Trial Procedures Manual. Refer to the Trial Flow Chart (Section 6) for the timing of laboratory assessments.

7.1.3.1 Laboratory Safety Evaluations (Hematology, Chemistry and Urinalysis)

Laboratory tests for hematology, chemistry, and urinalysis are specified in [Table 16](#). Except for analyses of biomarkers or other prognostic indicators (proteomics, genetics, transcriptional analysis, pharmacokinetics, antibodies), all tests will be analyzed locally.

Table 16 Laboratory Tests

Hematology	Chemistry	Urinalysis	Other
Hematocrit	Albumin	Blood	Pregnancy test (serum or urine) ^a
Hemoglobin	Alkaline phosphatase	Glucose	PT/INR
Platelet count	Alanine aminotransferase	Protein	aPTT
WBC (total and differential) ^d	Aspartate aminotransferase	Specific gravity	Total T3 or free T3, FT4, and TSH ^b
RBC	Bicarbonate ^c	Microscopic exam, if abnormal results are noted	B2 microglobulin G6PD (as necessary)
Absolute lymphocyte count ^d	Calcium		
	Chloride		
Absolute neutrophil count ^d	Creatinine		
	Glucose		
	LDH		
	Phosphorus		
	Potassium		
	Sodium		
	Total bilirubin		
	Direct bilirubin		
	Total protein		
	Uric Acid		
	Blood urea nitrogen		

^a Perform on women of childbearing potential only 72 hours prior to Day 1 of Cycle 1. All women who are being considered for participation in the trial, and who are not surgically sterilized or postmenopausal, must be tested for pregnancy within 72 hours of each cycle of trial treatment and 30 days post-treatment.

^b T3 is preferred; if not available free T3 may be tested.

^c If this test is not done as part of local standard of care, this test does not need to be performed.

^d Report % or absolute results per standard of practice. Report the results in the same manner throughout the trial.

Abbreviations: aPTT = activated partial thromboplastin time; G6PD = glucose-6-phosphate dehydrogenase deficiency; INR = international normalized ratio; LDH = lactic dehydrogenase; PT = prothrombin time; RBC = red blood cells; WBC = white blood cells.

7.1.3.2 Pregnancy Test

All women who are being considered for participation in the trial, and who are not surgically sterilized or postmenopausal, must be tested for pregnancy within 72 hours of each cycle of trial treatment and 30 days post-treatment. If a urine test is positive or not evaluable, a serum test will be required. Subjects must be excluded/discontinued from the trial in the event of a positive or borderline-positive test result.

7.1.3.3 Evaluations for Subjects with CLL

For subjects with CLL, at baseline assess for constitutional symptoms and analyze blood or serum as appropriate for the following (all analyses local). Repeat at post-baseline as needed (Section 6).

- Fluorescence in situ hybridization (FISH) or cytogenetics for del17p, del13q, del11q, trisomy 12,
- IgVH mutational status (mutated is $\geq 2\%$ difference from germline)
- CD38 (percentage of CLL cells expressing CD38)
- CD4, CD8
- Quantitative serum immunoglobulins (IgA, IgG, IgM)

7.1.3.4 Evaluations for Subjects with MM

For subjects with MM, baseline bone marrow analysis (local) will include morphology, immunohistochemistry, cytogenetics by standard karyotyping, and FISH panel. Additionally, baseline quantitative serum immunoglobulins (IgA, IgG, IgM) are required. Repeat these studies if post-baseline bone marrow is done (Section 6).

7.1.3.5 Pharmacokinetic/Pharmacodynamic Evaluations

Blood samples will be obtained to measure pharmacokinetics of serum dinaciclib on Cycle 3 Day 1 and of serum pembrolizumab as per the Trial Flow Charts (Section 6). If the infusion is being given through a central venous catheter, either arm may be used to obtain pharmacokinetic samples.

7.1.3.6 Blood Collection for Anti-pembrolizumab Antibodies

Sample collection, storage, and shipment instructions for serum samples will be provided in the procedure manual. Anti-pembrolizumab antibody samples should be drawn according to the collection schedule (Section 6). Every effort should be taken to collect samples at 30 days after end of treatment (or **before** the subject starts new anticancer therapy, **whichever comes first**) for pembrolizumab pharmacokinetic level and anti-pembrolizumab antibodies.

Sample collection, storage, and shipment instructions for plasma samples will be provided in the operations/laboratory manual.

7.1.3.7 Blood Collection for Correlative and Biomarker Studies

Any leftover samples from the correlative and biomarker blood studies will be stored for future biomedical research if the subject signs the Future Biomedical Research consent. Sample collection, storage, and shipment instructions for plasma samples will be provided in the operations/laboratory manual.

7.1.3.8 Planned Genetic Analysis Sample Collection

Sample collection, storage, and shipment instructions for Planned Genetic Analysis samples will be provided in the Procedures Manual. Samples should be collected for planned analysis of associations between genetic variants in germline/tumor DNA and drug response. If a documented law or regulation prohibits (or local IRB/Independent Ethics Committee [IEC] does not approve) sample collection for these purposes, then such samples should not be collected at the corresponding sites. Leftover DNA extracted from planned genetic analysis samples will be stored for future biomedical research only if subject signs the Future Biomedical Research consent.

7.1.3.9 Future Biomedical Research

The following specimens are to be obtained as part of Future Biomedical Research:

- DNA for future research
- Leftover bone marrow biopsy samples
- Leftover lymph node biopsies
- Leftover DNA and RNA from correlative studies
- Leftover plasma and serum from biomarker studies

7.1.4 Other Procedures

7.1.4.1 Withdrawal/Discontinuation

Subjects who discontinue/withdraw from treatment prior to completion of the treatment regimen should be encouraged to continue to be followed for all remaining study visits.

When a subject discontinues/withdraws from participation in the trial, all applicable activities scheduled for the final trial visit should be performed at the time of discontinuation. Any adverse events which are present at the time of discontinuation/withdrawal should be followed in accordance with the safety requirements outlined in Section 7.2 - Assessing and Recording Adverse Events.

7.1.4.1.1 Withdrawal From Future Biomedical Research

Subjects may withdraw their consent for Future Biomedical Research and have their specimens and all derivatives destroyed. Subjects may withdraw consent at any time by contacting the principal investigator for the main trial. If medical records for the main trial are still available, the investigator will contact the Sponsor using the designated mailbox ([contact]), and a form will be provided by the Sponsor to

obtain appropriate information to complete specimen withdrawal. Subsequently, the subject's specimens will be removed from the biorepository and be destroyed. A letter will be sent from the Sponsor to the investigator confirming the destruction. It is the responsibility of the investigator to inform the subject of completion of destruction. Any analyses in progress at the time of request for destruction or already performed prior to the request being received by the Sponsor will continue to be used as part of the overall research trial data and results. No new analyses would be generated after the request is received.

In the event that the medical records for the main trial are no longer available (e.g., if the investigator is no longer required by regulatory authorities to retain the main trial records) or the specimens have been completely anonymized, there will no longer be a link between the subject's personal information and their specimens. In this situation, the request for specimen destruction cannot be processed.

7.1.4.1.2 Lost to Follow-up

If a subject fails to return to the clinic for a required trial visit and/or if the site is unable to contact the subject, the following procedures are to be performed:

- The site must attempt to contact the subject and reschedule the missed visit. If the subject is contacted, the subject should be counseled on the importance of maintaining the protocol-specified visit schedule.
- The investigator or designee must make every effort to regain contact with the subject at each missed visit (eg, phone calls and/or a certified letter to the subject's last known mailing address or locally equivalent methods). These contact attempts should be documented in the subject's medical record.
- Note: A subject is not considered lost to follow-up until the last scheduled visit for the individual subject. The amount of missing data for the subject will be managed via the pre-specified data handling and analysis guidelines.

7.1.4.2 Blinding/Unblinding

This is an open label trial; there is no blinding for this trial.

7.1.4.3 Domiciling

Subjects with CLL or DLBCL will report to the clinical research unit on Day -1 prior to the scheduled day of trial drug administration on Cycle 1 Day 1 and remain in the unit until approximately 10 hours post-dose on Day 1. At the discretion of the investigator, subjects may be requested to remain in the clinical research unit longer.

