5.2.1.3.1 Premedication for Dinaciclib for rrCLL and rrDLBCL

Note: The rrCLL cohort was closed to enrollment on 30-APR-2019 due to lack of accrual, and all subjects with rrCLL have discontinued from treatment. Remaining subjects with rrCLL are in survival follow-up.

Premedication and supportive care for dinaciclib is required for all subjects with rrCLL and rrDLBCL and is summarized in [Table 6](#).

For subjects with rrCLL and rrDLBCL who will receive rasburicase as a premedication, glucose-6-phosphate dehydrogenase deficiency (G6PD) testing should be completed locally when required in subjects at higher risk of G6PD deficiency (eg, subjects of African or Mediterranean ancestry). These subjects should be tested and found to have adequate levels before treatment with rasburicase.

Subjects with rrCLL and rrDLBCL will be admitted to the inpatient service to begin Cycle 1 so as to facilitate aggressive hydration prior to and close monitoring during the first dose of dinaciclib on Cycle 1 Day 1 and Day 2.

Monitor the subject for laboratory TLS and cytokine release syndrome (CRS) during and after the first administration of dinaciclib as described in Section 12.5 for Supportive Care Guidelines for TLS Prevention and Management.

Absent severe TLS complicating dinaciclib administration, subsequent therapy will be delivered on an outpatient basis (Section 12.5).

Table 6 Premedication for Dinaciclib for rrCLL and rrDLBCL

	Agent/Drug	Dose	Route	Schedule
Premedication ^{a, b}	Rasburicase	0.2 mg/kg or per institutional standard	IV	2 hrs prior to C1D1 dose; thereafter at investigator discretion
	Antiemetic with a serotonin-receptor antagonist	Per drug label or institutional standard	Per drug label or institutional standard	Prior to each dose according to label or institutional standard
	Dexamethasone	12 mg	IV	30 min prior to each dose
	Kayexalate (or equivalent)	30 g	PO	At least 30 min prior, if serum potassium ≥ 4.0 mmol/L in Cycle 1 only
Supportive Care ^a	Oral phosphate binder, such as calcium acetate or equivalent	Calcium acetate 1334 mg	Calcium acetate PO	12 and 2 hrs prior to each dose

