	IV hydration with 0.45% sodium chloride sterile solution, or other appropriate IV solution	Subjects with CLL and DLBCL: C1D1: 200 ml/hr for ≥ 10 hrs prior to initiation of, during and continuing for ≥ 10 hrs after completion of dinaciclib infusion. Subsequent infusions: 200 ml/hr for ≥ 1 hr prior to initiating, during and continuing for ≥ 2 hrs after completion of dinaciclib infusion.		
	Herpes zoster virus prophylaxis (valacyclovir 500 mg PO daily or acyclovir 400 mg PO BID or institutional standard)			
	Pneumocystis pneumonia (previously known as P. carinii) prophylaxis (Bactrim DS 1 tablet PO BID Monday-Wednesday-Friday or dapsone 100 mg PO daily or institutional standard).			
	Subjects with documented evidence of current/previous hepatitis B should receive antiviral prophylaxis during and for 6 months beyond last treatment.			
^a Institutional equivalents may be used for all premedications with the exception of rasburicase. Supportive care guidelines should be followed as above; however, if subject clinical condition requires modification to the dose, route, or schedule then institutional standards may be used only after consultation with the Sponsor . ^b If TLS is not observed, these guidelines may be revised.				
Abbreviations: BID = twice daily; C1D1 = Cycle 1 Day1; CLL = chronic lymphocytic leukemia; DLBCL = diffuse large B-cell lymphoma; IV = intravenous; PO = oral; TLS = tumor lysis syndrome.				

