12.4 ECOG Performance Status

Grade	Description
0	Normal activity. Fully active, able to carry on all pre-disease performance without restriction.
1	Symptoms, but ambulatory. Restricted in physically strenuous activity, but ambulatory and able to carry out work of a light or sedentary nature (e.g., light housework, office work).
2	In bed <50% of the time. Ambulatory and capable of all self-care, but unable to carry out any work activities. Up and about more than 50% of waking hours.
3	In bed >50% of the time. Capable of only limited self-care, confined to bed or chair more than 50% of waking hours.
4	100% bedridden. Completely disabled. Cannot carry on any self-care. Totally confined to bed or chair.
5	Dead.
* As published in Am. J. Clin. Oncol.: Oken, M.M., Creech, R.H., Tormey, D.C., Horton, J., Davis, T.E., McFadden, E.T., Carbone, P.P.: Toxicity And Response Criteria Of The Eastern Cooperative Oncology Group. Am J Clin Oncol 5:649-655, 1982. The Eastern Cooperative Oncology Group, Robert Comis M.D., Group Chair.	

12.5 Recommended Supportive Care Guidelines for Tumor Lysis Syndrome Prevention and Treatment in Subjects with CLL and DLBCL

1. Subjects with CLL and DLBCL will be admitted to the inpatient service the day prior to dinaciclib treatment for a minimum of the first treatment (C1D1 dose).
2. Premedication and IV hydration for dinaciclib for CLL and DLBCL are described in Section 5.2.1.3.1 (Table 6).
3. Using the Cairo-Bishop definition of laboratory TLS, K, calcium, potassium, and uric acid will be evaluated at 3 and 5 hours after the start of the first dinaciclib infusion (C1D1) as part of a TLS work-up (Section 5.2.1.3.3). Subjects with a positive TLS work-up should remain in the hospital and follow-up should be initiated. If necessary, subjects must be admitted overnight for observation.
 - If serum potassium > 4.5 mmol/L, then the subject should receive a 30 g dose of Kayexalate (or equivalent).
 - If serum potassium > 5.0 mmol/L, then the subject should receive 10 units of IV regular insulin and one ampule of D50 IV. During this time period, trial treatment administration should be discontinued.
 - If serum potassium > 5.5 mmol/L, then the subject should be considered for emergent intermittent or continuous hemodialysis.

During this time period, trial treatment administration should be discontinued.

Subjects who do not have laboratory TLS may receive Dose 2 (Day 8) of Cycle 1, as well as all subsequent therapies, as an outpatient.

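### The protocol gives conflicting instructions on how long rrDLBCL subjects stay under observation after the first dinaciclib dose

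*Combined protocol and SAP*

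**What the plan says.** Five places in the combined protocol and SAP bear on the stay around Cycle 1 Day 1.

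- **Section 7.1.4.3 (Domiciling).** Subjects with CLL or DLBCL report on Day -1 and "remain in the unit until approximately 10 hours post-dose on Day 1". Then: "At the discretion of the investigator, subjects may be requested to remain in the clinical research unit longer".
- **Section 5.2.1.3.1.** Subjects with rrCLL and rrDLBCL "will be admitted to the inpatient service to begin Cycle 1", to allow hydration and "close monitoring during the first dose of dinaciclib on Cycle 1 Day 1 and Day 2". Monitoring for tumor lysis syndrome (TLS) and cytokine release is to be done "as described in Section 12.5 for Supportive Care Guidelines for TLS Prevention and Management".
- **Table 6 (in Section 5.2.1.3.1).** "Premedication and supportive care for dinaciclib is required for all subjects with rrCLL and rrDLBCL". On Cycle 1 Day 1, intravenous hydration runs for at least "10 hrs after completion of dinaciclib infusion". A footnote allows departures only after the Sponsor has been consulted.
- **Sections 5.2.1.3.3 and 12.5 item 3.** TLS bloods are taken 3 and 5 hours after the first infusion starts, and a subject with a positive work-up stays in hospital. Both sections then add that overnight admission for observation is to happen where necessary.
- **Section 12.5, items 1, 7 and 8.** Subjects with CLL and DLBCL "will be admitted to the inpatient service the day prior to dinaciclib treatment for a minimum of the first treatment". Item 7 allows discharge home on the morning after the first infusion, once the treating physician has seen the chemistry results. Item 8 puts the first dose early in the day.

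**The concern.** A site that asks when a DLBCL subject with a negative TLS work-up may leave finds two answers. Section 7.1.4.3 gives the evening of Day 1 as the default. Sections 5.2.1.3.1 and 12.5 item 7 point to the next morning. Section 7.1.4.3 does not mention Day 2 or a chemistry review, and it refers to neither of the other sections.

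What is at stake is observation time in the period that Section 12.5 itself singles out as the one of greatest tumor lysis risk. The TLS definition in Section 5.2.1.3.3 runs to 7 days after the start of dinaciclib, but the flow chart schedules TLS bloods only at 3 and 5 hours. For a subject whose early bloods are clean, the next-morning review in item 7 is the remaining inpatient check, and a site working from Section 7.1.4.3 could omit it. Sites could follow different sections and each claim compliance.

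**Working it through.** The plan gives no figure to reproduce. The check is a comparison of the texts plus clock arithmetic.

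**Texts side by side**

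| Place | Overnight stay after the first dose? | Force of the wording |
|---|---|---|
| 7.1.4.3 | Not by default; longer at discretion | Instruction |
| 5.2.1.3.3 and 12.5 item 3 | Where necessary | Conditional |
| 5.2.1.3.1 | Implied by monitoring on Day 1 and Day 2 | Mandatory admission; the Day 2 phrase is loosely worded |
| 12.5 item 1 | Not stated; admission for at least the first treatment | Section headed as recommended |
| 12.5 item 7 | Yes; discharge next morning | Permissive verb, in a section headed as recommended |

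Keeping every subject overnight satisfies all five rows. Releasing at 10 hours satisfies the first two, does not fit the third or the fifth, and is left open by the fourth.

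**When the 10 hours end, relative to Table 6 hydration**

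Inputs:
- Minimum dinaciclib infusion of 2 hours (Section 5.2.1.3).
- Hydration for at least 10 hours after the infusion ends (Table 6).
- Pembrolizumab given first (Section 5.2.1.1), nominally over 30 minutes (Section 5.2.1.2).

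Let S be the start of dinaciclib. The infusion ends at S + 2 at the earliest, so hydration ends at S + 2 + 10 = S + 12 at the earliest.

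- Counted from the end of dinaciclib: release at S + 2 + 10 = S + 12. Shortfall 12 - 12 = 0 hours.
- Counted from the start of dinaciclib: release at S + 10. Shortfall 12 - 10 = 2 hours.
- Counted from the start of pembrolizumab: S is at least 0.5 hours later, so hydration ends no earlier than 12.5 hours on that clock. Shortfall at least 12.5 - 10 = 2.5 hours.

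Only the first reading meets Table 6, and it does so with no margin.

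**Difference in observation time**

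This uses the reading most favourable to Section 7.1.4.3, release 10 hours after dinaciclib ends. Item 8 says only that the dose comes early in the day, so the clock times are assumptions: start and next-morning discharge each at 08:00, varied from 07:00 to 10:00.

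| Start | Infusion ends | Release, 7.1.4.3 | Discharge, item 7 | Stay after infusion, item 7 | Difference |
|---|---|---|---|---|---|
| 08:00 | 10:00 | 20:00 | 08:00 | 22 h | 22 - 10 = 12 h |
| 10:00 | 12:00 | 22:00 | 07:00 | 19 h | 19 - 10 = 9 h |
| 07:00 | 09:00 | 19:00 | 10:00 | 25 h | 25 - 10 = 15 h |

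In every case the release falls on the evening of Day 1.

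**The case against.** The strongest reply is that Section 7.1.4.3 is not out of line. Two other places treat an overnight stay as conditional, which fits a default of about 10 hours with discretion to extend. Section 12.5 is headed as recommended, item 7 uses a permissive verb, and item 1 sets the inpatient minimum at the first treatment rather than a night. In Section 5.2.1.3.1 the Day 2 phrase is attached to the first dose, yet no dinaciclib is given on Day 2 and the flow chart has no Day 2 visit. Read as 10 hours after the infusion ends, Section 7.1.4.3 matches Table 6 exactly.

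Most of this stands. A reader might infer that the protocol requires an overnight stay and that Section 7.1.4.3 alone departs from it. The documents do not support that, because the conditional sentence in Sections 5.2.1.3.3 and 12.5 item 3 sits on the same side as Section 7.1.4.3. A reader might also infer that subjects are sent home that evening. Section 7.1.4.3 speaks of a clinical research unit and the other sections of an inpatient service. The documents do not say whether these are the same place, so going home is a permitted reading and not a stated one. Nor is the subject left unprotected: the 3- and 5-hour bloods, the hold for a positive work-up, the required hydration and the investigator's discretion apply on either reading.

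The reply does not remove the conflict. Sections 5.2.1.3.1 and 12.5 item 1 admit every such subject whatever the work-up shows, and item 7 names a discharge time that Section 7.1.4.3 does not share. That overnight stay appears as conditional in some places and as the expected course in others is the inconsistency itself.

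**Conclusion.** The inconsistency is real and modest. The protocol divides on whether a DLBCL subject with a negative work-up stays the night after the first dinaciclib dose, and the 10-hour rule lacks a defined starting point.

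The shortfall of about 2 hours against Table 6 arises only if the clock starts with the dinaciclib infusion, and it is slightly larger if the clock starts with pembrolizumab. The difference of about 12 hours (range 9 to 15) rests on assumed clock times. It measures observation time and is not a clinical effect.

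The reach is narrow. rrMM subjects were dosed as outpatients, and both rrMM and rrCLL subjects are off treatment. No closure note covers rrDLBCL, but the current amendment was issued so that the study could end, and the documents do not say how many first doses remain, if any. No endpoint, sample size or estimate is affected. This is a cheap improvement, not a fault that threatens the trial.

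**What to change.** Two linked changes are needed. Amending Section 7.1.4.3 alone would leave the conditional sentence elsewhere in sharper conflict with it.

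1. In Section 7.1.4.3, replace the 10-hour release with: *remain in the unit (inpatient service) until the morning of Cycle 1 Day 2, after Table 6 post-infusion hydration is complete and the treating physician has reviewed chemistry results (see Section 12.5 item 7)*. This removes the undefined starting point and settles the difference in location wording.
2. In Sections 5.2.1.3.3 and 12.5 item 3, replace the conditional overnight sentence with a statement that subjects with a positive TLS work-up stay beyond the Day 2 morning until it resolves.

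The cost is edits in three places and an overnight stay at any site now using the 10-hour release, a stay that Sections 5.2.1.3.1 and 12.5 item 7 already contemplate. The wording repeats item 7's review condition and does not by itself add a blood draw. If the sponsor intends a Day 2 sample, the flow chart should show it.
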